# Flowsheet

## Phase II study of definitive radiochemotherapy for locally advanced squamous cell cancer of the vulva: an efficacy study

# **1. Background and introduction**

## **1.1 General introduction**

Cancer of the vulva is a relatively rare disease with an annual incidence of 2-3 per 100.000 women. The main histological subtype is squamous cell cancer (75%) followed by basal cell cancer (15%) and other types like adenocarcinoma, melanoma and sarcoma's in 10% of cases [1]. In the Netherlands each year 150-200 new patients are diagnosed with vulvar cancer [2]. A steep rise in age specific incidence rate is seen above 65 years with the majority of patients being 75 years or older. About 70% of patients with squamous cell cancer (SCC) of the vulva present with a local tumor confined to the vulva (cT1/T2). These patients are usually treated with a radical local excision and uni- or bilateral inguinal femoral lymph node dissection [3]. When lymph nodes are negative (70-80% of patients), survival is high with a 5 year disease specific survival of 80-90%. When the groin nodes are positive survival decreases from 30% in case extra capsular tumor is found, till 60% in case the lymph node metastases are intracapsular [4].

In 30% of the patients tumors are classified as T3/T4 tumors with either extension of the tumor to the vagina, the proximal urethra or anus (cT3) or extension to the upper urethra or bladder, upper anal canal or rectum or the tumor is fixed to the pubic bone (cT4). Those cases in which the typical radical surgical excision of the vulva will not remove the cancer with adequate margins are considered to be locally advanced or cT3/T4 vulva carcinoma. The primary tumor causes serious local problems such as pain while sitting, discharge, bleeding from necrotic tumor and a foul odor. Positive lymph nodes are found in 50%-60% of patients with T3/T4 tumors. Frequently these nodes are ulcerating and or fixed to the femoral vessels in the groin. These patients presenting with locally advanced disease (cT3/T4) pose a specific problem regarding the treatment.

## **1.2 Surgery for locally advanced vulvar cancer**

In patients with T3 vulvar cancer, literature data show a 75% local control rate while a survival from 64% to 77% can be achieved after primary surgery (Addendum 1, Table 1). Survival decreases dramatically to 40% in the presence of nodal metastases in the groin [10]. In patients with locally advanced disease local control can only be accomplished by extensive surgical resections. Partial removal of the distal urethra and partial sfincter resections can be performed with preservation of continence, dependant on the extent of the resection [11]. However, when extensive anal and/or urethral involvement is present radical surgery or exenterations will definitely result in stoma formation. Other than the stoma formation also postoperative morbidity and mortality is a significant problem in these patients. Morbidity such as serious wound breakdown, infection, leg edema and lymphocysts is frequently observed after extensive surgery for advanced vulvar cancer [12].

## **1.3 Radio (chemo) therapy for locally advanced vulvar cancer**

In anal cancer radiotherapy combined with chemotherapy is very efficacious as sphincter sparing therapy in preventing colostomies [13]. Radiotherapy with or without chemotherapy has also proven it's efficacy in the treatment of vulvar cancer [14]. Collated literature data show a somewhat lower local control rate of 40% after radiochemotherapy compared with surgery (addendum 1, Table 2). But the interpretation of the literature is very difficult because of the heterogeneity of inclusion criteria and differences in end-point or assessment of tumor response. It is clear that radiotherapy in moderate doses combined with chemotherapy, followed by organ sparing surgery has shown its' efficacy in preventing stoma formation [22]. Of 71 patients with locally advanced vulvar cancer (carcinoma of the vulva with unresectable

N2/N3 groin lymph nodes), treated with a combination of 4760 cGy radiotherapy (daily fractions 2 x 170 cGy and given as split course with an interval of 1½ to 2½ weeks) combined with concurrent chemotherapy (cisplatin and 5-FU) resulted in the prevention of either a uro- or colostomy in 49 of 50 patients, although postoperative wound complications were frequent. Others have also shown that the combination of induction radiochemotherapy followed by surgery in the previously irradiated area results in the prevention of stoma formation but can also result in significant wound healing problems and treatment related mortality [23]. Most of the studies as mentioned before used moderate doses of radiotherapy because of poor skin tolerability (inflammation, dry and moist desquamation, fibrosis) of the vulvar area. Some studies suggested a better local control when the gross tumor volume was irradiated with doses above 50 Gy [24]. Therefore, in order to increase local control, either additional surgery or higher radiation doses are warranted.

#### **1.4 Treatment of the inguino femoral lymph nodes**

One of the additional problems in patients with locally advanced vulvar cancer is the high incidence of concomitant advanced regional (inguinal) disease. In patients with T3/T4 vulvar cancer the incidence of metastases in the inguino femoral lymph nodes can be as high as 60%. A substantial number of these patients have clinically palpable “bulky” nodes (cN1/2). From various studies it becomes clear that the presence of inguino femoral metastases, especially cN1/2 nodes is the most important significant predictor for survival.

On the basis of the available literature data most authors conclude that radiotherapy is a proper treatment for microscopical (residual) disease in the groin, but not for gross disease [25]. The only study addressing the problem of the efficacy of radiotherapy for the groin in case cN1/2 nodes are present showed that out of 46 patients with vulvar cancer and (inoperable) N2/3 inguinal disease, 37 patients could have surgery after chemoradiation. Finally 15 out of 37 patients operated upon had a pathological complete response [26]. There are no data on definitive treatment with radiochemotherapy for cN1/2 groin nodes.

#### **1.5 Rationale for chemotherapy regimen**

When combining chemotherapy and radiotherapy several chemotherapeutic regimens have been reported for a variety of cancer types. In vulvar cancer 5-FU has been used in combination with cisplatin or Mitomycine C with acceptable toxicity, but the studies are small and median age is lower than might be expected in the general population with vulvar cancer [27, 28, 29 and 30]. And especially in an older patient population the nephrotoxicity of cisplatin might be of concern. Mitomycin C is not introduced in the newer chemoradiation studies in rectal, cervical or head- and neck cancer, because of its toxicity profile. Especially the extended thrombocytopenia makes repeated administration impossible.

Oral fluoropyrimidines, because of their ease of administration, constitute an attractive alternative for fluorouracil. Capecitabine, an oral fluoropyrimidine carbamate, has been designed with the aim of delivering 5-FU predominantly to the tumour cells [31, 32 and 33]. Capecitabine is rapidly and extensively absorbed as an intact molecule and is metabolized to 5-FU in three steps. Because each step of metabolic conversion occurs successively, and a greater specificity for tumour cells is present, capecitabine potentially reduces systemic exposure to 5-FU while maximizing the dose-intensity of 5-FU within tumour tissue. Several clinical trials in breast and colorectal cancer have demonstrated a more favourable toxicity profile with capecitabine than the infused fluoropyrimidines although the incidence of the hand-foot syndrome is slightly higher [34, 35 and 36].

The combination of capecitabine with radiotherapy has been studied in several phase I studies. A dosage of 825 – 1000 mg/sqm bid administered without a break during a conventional

radiotherapy period of 6 weeks has been shown a feasible and well-tolerated regimen [37, 38, 39 and 40].

Because of the intensive radiotherapy regimen in this relatively older patient population monotherapy with capecitabine with a treatment interruption has been selected for the combined modality approach in this study.

### **1.6 Rationale of the study**

Exenterative surgery for locally advanced vulvar cancer results in a reasonable local control but only at the prize of considerable morbidity including stoma formation. There is very limited experience with radiochemotherapy followed by surgery for locally advanced vulvar cancer. The studies available show a decreased need for stoma formation but still accompanied with considerable morbidity, e.g. especially wound healing problems. More sophisticated radiotherapy targeting and promising chemotherapy schemas have been developed in the past years. However, so far the combination has not been studied substantially in locally advanced vulvar cancer patients. This study will deliver experience with modern radiochemotherapy options and aims at a reasonable local control precluding the need for local salvage surgery.

## **2. Objectives of the study**

### **2.1 primary objective**

The primary objective is to gain experience with primary radiochemotherapy and to determine the locoregional response rate at 12 weeks after radiochemotherapy and after groin dissection for cN1,2 patients.

### **2.2 secondary objectives**

The secondary objective would be to determine short-term morbidity defined as desquamation of the skin, infection, long-term morbidity defined as edema, fibrosis, the incidence of fecal and or urinary continence, and or incidence of reconstructive surgery performed and treatment related mortality. Longterm morbidity and the rate of locoregional recurrences will be evaluated at 24 months after the end of radiochemotherapy.

### **2.3 endpoints**

#### **Primary endpoints**

- locoregional control rate defined as clinically or pathologically proven absence of tumor (CR according to RECIST criteria) in the vulvar area, groins and/or pelvis 12 weeks after the end of radiochemotherapy and after groin dissection in cN1,2 patients.

#### **Secondary endpoints**

- morbidity and treatment related toxicity
- incidence of fecal and/or urinary continence and/or reconstructive surgery performed
- locoregional recurrence rate at 24 months after the end of radiochemotherapy

### **3. Patient selection criteria**

#### **3.1 Eligibility criteria:**

- squamous cell cancer of the vulva with locally advanced disease not curable with surgery unless extensive reconstructive surgery or a colostomy or urostomy is performed
- Amenable to curative treatment
- No disease present outside the pelvis
- Performance status WHO 0-2
- Patients must be fit enough to undergo salvage surgery after chemo radiotherapy
- Measurable disease at least locally (vulvar area)
- Pretreatment laboratory values
  - Hb > 6.5 mmol/l
  - Neutrophil count > 1.5 x 10^9/l
  - Platelets ≥ 100 x 10^9/l
  - Bilirubin < 25 μmol/l
  - Adequate liver function: ALAT and ASAT < 2.5 upper normal limit
  - Alkaline phosphatase < 2.5 upper normal limit
- No upper age limit specified. Patients should mentally, physically and geographically be able to undergo treatment and follow-up
- Patients must be > 18 years old
- Written informed consent
- No psychosis, CNS disease or other expected difficulty for follow-up
- No active uncontrolled infection
- No concomitant or previous malignancy other than basal cell carcinoma of the skin or CIN of the cervix

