### *5.2.1 Dose modifications*

If a patient experience a grade 2 or 3 toxicity that is considered possibly related to capecitabine treatment or clearly not related solely to radiation, capecitabine treatment will be interrupted. When the toxicity has resolved to grade 0 to 1, treatment will be restarted without dose adjustment. However, in the case of grade 3 nausea/vomiting or diarrhea not resolving to grade 0 to 1 within 2 days of interruption despite symptomatic treatment, capecitabine treatment will be restarted with a 25 % dose reduction. On the recurrence of toxicity at grade 2 or more severe intensity, treatment will be again interrupted until the toxicity has resolved to grade 0 to 1. Treatment will then be restarted with a dose reduction of 25%. All dose modifications and symptomatic treatments should be documented.

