### *5.4.2 Chemotherapy:*

Most side effects are on the short term and constitute of vomiting, bone marrow depression, diarrhea, mild alopecia, and hand-foot syndrome.

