### **6.1 Before treatment start**

The following examinations should be performed within 4 weeks prior to treatment:

- Medical history
- Physical and gynecological examination
- WHO performance status
- TNM stage

- A photograph of the tumor with an adjacent ruler must be taken.
- Pathology of the primary tumor.
- The primary tumor must be localized exactly, measured in two dimensions and the margins towards the vagina, urethra, anus and clitoris must be stated in mm.
- The clinical description of the groin nodes must include: number of palpable nodes, side of nodes, size, mobility and whether or not a lymphangitis is present.
- CT, MRI or US scan of the groin region (If CT/MRI/US scan shows a suspicious lymph node or in case of clinical suspicion, FNA should be performed).
- Chest X-ray
- Routine blood tests (leukocytes, platelets, Hb, HT)
- Serum creatinine, ASAT, ALAT, bilirubin and alkaline phosphatase
- Socio-demographic data

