## **6.2 During radiochemotherapy**

- Laboratory examination weekly: haematology: Hb, Ht, platelets, leucocytes; cchemistry: Na, K, Ca, Alb, Creatinine, Bilirubin, gGT, AF, ASAT, ALAT, LDH. Creatinin clearance if plasma creatinine > 100 umol/l.
- Morbidity according to CTCAE criteria version 3 (addendum 2, page 23)
  - signs of early toxicity (eg skin)
  - monitoring of other radiotherapy-related toxicity (bowel, GU)

During radiotherapy patients will be seen weekly by the radiation oncologist and medical oncologist to monitor morbidity and treatment related toxicity

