## 6.6 Summary Table

Required investigations	Prestudy	After initial surgery*	During radiochemotherapy	After radiochemotherapy	After secondary surgery**	During follow up
						yr. 1-2: 3-monthly yr 2-5: 6-monthly
Day	-28 tot 0	-28 tot 0	Start day 0  weekly	4, 8 and 12 weeks after last radiochemotherapy	> 12 weeks after last radiochemotherapy	
History	X 1					
Phys/gyn exam	X 1/ 2			X 1/2		X 1/2
WHO	X 1		X 2/ 3	X 2		
TNM	X 1					
Photo	X 1			X 2		
Chest X-ray	X 1					
CT/MRI/US	X 1			X 1/2 ***		
Haematology	X 1		X 2/ 3	X 1		
Biochemistry	X 1		X 2/ 3	X 1		
Path lymph nodes		X 1			X 1	
Path primary tumor	X 1				X 1	
Short-term morb		X 1	X 2/ 3	X 2	X 1	
Long term morb						X 1/2

\* Only when upfront surgery is performed for clinically (and pathologically confirmed) positive groin lymph node metastases

\*\* Only when salvage surgery for the primary or groin dissection is performed

\*\*\* Optional

- 1) gynecologic oncologist
- 2) radiation oncologist
- 3) medical oncologist

 Haematology: Hb, Ht, platelets, leucocytes  
Chemistry: Na, K, Creatinin, ureum, Bilirubin, gGT, AF, ASAT, ALAT, LDH.  
Creatinin clearance if plasma creatinin > 100 umol/l.

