### Safety Monitoring

Adverse events will be monitored on an ongoing basis and their frequencies reported semi-annually. Toxic effects will be categorized using the NCI Common Terminology Criteria for Adverse Events, Version 3.0. The worst event for each patient will be described. Both events related and unrelated to treatment will be captured.

Clinical and laboratory data will be tabulated and compared to normal ranges for the institution.

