### **Questions on the registration checklist:**

Standard questions: Name (number) of institution, patients' initials (max 3), patients' sequential study number

Protocol specific questions: all eligibility criteria, confirmation of informed consent, date of informed consent.

A patient can be registered after verification of eligibility (form 3 eligibility form) by [contact] or [contact], before the start of treatment.

At the end of the registration procedure, a number will be allocated to the patient (patient sequential study number) send by the study secretariat by fax or email. This number has to be recorded on form 3 (eligibility form), along with the date of the registration. The study identification number attributed to the patient at the end of the registration procedure identifies the patient and must be reported on all case forms.

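### The protocol sets a neutrophil limit for entry, but no required blood panel includes neutrophils, so nothing prompts a neutrophil count during radiochemotherapy and neutropenia would be recorded only where a site happens to measure it

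*Protocol*

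**What the plan says.** Section 3.1 lists, among the pretreatment laboratory values, "Neutrophil count > 1.5 x 10" (to the ninth power, per litre). This is the only mention of neutrophils in the protocol. Section 10 carries the criterion into registration: the checklist contains "Protocol specific questions: all eligibility criteria", and eligibility is verified before the patient is registered.

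Three places state which blood counts are required:

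- 6.1, before treatment: "Routine blood tests (leukocytes, platelets, Hb, HT"
- 6.2, during radiochemotherapy: "Laboratory examination weekly: haematology: Hb, Ht, platelets, leucocytes"
- 6.6, footnote to the summary table: "Haematology: Hb, Ht, platelets, leucocytes"

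Four other places bear on how blood counts are used. Section 5.4.2 describes the expected effects of the chemotherapy: "Most side effects are on the short term and constitute of vomiting, bone marrow depression", among others. Section 5.2.1 begins its modification rule with "If a patient experience a grade 2 or 3 toxicity that is considered possibly related to capecitabine treatment", and ties interruption and restart of capecitabine to the grade. Under Safety Monitoring in section 8, "Toxic effects will be categorized using the NCI Common Terminology Criteria for Adverse Events, Version 3.0". Section 2.3 makes morbidity and treatment-related toxicity a secondary endpoint.

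**The concern.** The entry criterion and the required tests do not match. The white-cell limit in 3.1 is on neutrophils, while the only white-cell measure in any required panel is the total leukocyte count. The total does not determine the neutrophil count.

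The consequence lies mainly on treatment. The protocol expects marrow depression, uses toxicity grades to steer capecitabine and reports graded toxicity as a secondary endpoint, yet after registration it never asks for the value needed to grade neutropenia. In a multi-centre study, the recorded frequency of neutropenia would then reflect which laboratories run a differential by habit as well as what the treatment does. A low recorded rate could not be told apart from a low rate of measurement.

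**Working it through.** There is no planned figure to reproduce, so the check is a comparison of sections, followed by two small pieces of arithmetic.

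**Step 1: match each laboratory criterion in 3.1 to a test in 6.1.**

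| Criterion in 3.1 | Test listed in 6.1? |
|---|---|
| Haemoglobin | yes |
| Neutrophils | no (leukocytes only) |
| Platelets | yes |
| Bilirubin | yes |
| ALAT and ASAT | yes |
| Alkaline phosphatase | yes |

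Neutrophils are the only laboratory criterion without a matching test. That looks like an oversight, not a choice.

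**Step 2: count the haematology lists that include neutrophils or a differential.** 6.1: no. 6.2: no. 6.6 footnote: no. Result: 0 of 3. Each list spells out its components, so a differential cannot be read into a general term such as full blood count.

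**Step 3: can leukocytes stand in for neutrophils?** Neutrophils = leukocytes x neutrophil share. The inputs here are assumed for illustration and do not come from the protocol. With leukocytes of 3.5 x 10⁹/l:

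- share 40%: 3.5 x 0.40 = 1.40, which fails the limit in 3.1
- share 65%: 3.5 x 0.65 = 2.28, which meets it

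The share at which the limit is crossed is 1.5 / 3.5 = 43%. The same leukocyte value is therefore compatible with either answer.

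**Step 4: what can be graded on treatment from the 6.2 list?** Leukocytes allow leukopenia to be graded, platelets thrombocytopenia, and haemoglobin anaemia. Neutropenia needs a neutrophil count and cannot be graded.

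**Step 5: number of draws at which the count is not mandated.** Inputs: a planned radiotherapy time of 7 weeks (5.1), weekly laboratory tests (6.2), and 42 patients in stage 1 and 68 in total (section 8). One draw per week is assumed for every patient.

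- full accrual: 68 x 7 = 476
- stop after stage 1: 42 x 7 = 294

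These are draws for which the protocol does not require the value, and so upper limits on the number lacking it. Haematology scheduled after radiochemotherapy in 6.6 is not counted.

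**The case against.** The strongest reply concerns eligibility. A reader might infer that the neutrophil criterion cannot be verified. The protocol does not support that: 3.1 itself calls for a pretreatment neutrophil value, and section 10 turns every criterion into a checklist item to be verified before registration. A site that follows the protocol must therefore order the count, and no ineligible patient enters through this gap unless the checklist also fails. For entry, 6.1 is an incomplete list and nothing more. This part of the reply stands.

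A reader might also infer that the rule in 5.2.1 cannot operate, or that haematological toxicity as a whole will be understated. Neither follows. The rule covers any toxicity of the stated grade that may be related to capecitabine; the only toxicities it names are nausea or vomiting and diarrhoea. Leukocytes, platelets and haemoglobin are measured weekly, so marrow depression is monitored. What is lost is neutropenia that the leukocyte grade does not show. How often that would happen cannot be worked out here, because Addendum 2 only links to CTCAE version 3 and does not reproduce its grades. Sections 2.2 and 7.2 also put the emphasis of short-term morbidity on other toxicities, including skin toxicity and infection.

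Finally, 476 could be read as the number of draws that will have no neutrophil value. It is not: nothing forbids a differential, and some sites may run one routinely. The case report forms are developed separately and are not shown, so whether they already have a neutrophil field is unknown.

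These points limit the size of the problem. They do not answer the on-treatment gap: after registration, nothing in the protocol prompts a neutrophil count.

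**Conclusion.** The inconsistency holds. A neutrophil limit is set in 3.1, and 0 of the 3 required haematology lists include the test. For entry the effect is minor, because other sections oblige the site to obtain the value. On treatment it has substance: a site that does exactly what is listed cannot grade neutropenia, so recorded neutropenia would depend on local laboratory habit. The count is not mandated at up to 476 weekly draws with full accrual, or 294 if the trial stops after stage 1, assuming one draw in each of 7 weeks for every patient.

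The damage is confined to one component of the toxicity endpoint and to the part of the grade-based rule that would depend on neutropenia. The direction of any error is towards too few recorded cases; its amount cannot be estimated from the protocol. The primary endpoint and the two-stage design are not touched. This is a cheap correction worth making, not a flaw that threatens the trial's main conclusion.

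**What to change.** Reconcile the test lists with 3.1. Add neutrophil count, from the same blood sample, to the haematology panel in 6.1, in 6.2 and in the footnote to 6.6. Check that the case report form has a field for it at baseline and at each on-treatment draw, so that the entry criterion can be audited and neutropenia graded under CTCAE version 3.0 in the same way at every centre.

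The cost is three wording changes and, if the field is missing, one addition to the case report form. The samples are already taken, so the extra laboratory and data-entry burden is negligible. No change to the eligibility threshold or to the capecitabine rule is proposed.
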